## 9.2 Study Assessments

Study assessments will be completed as per Section 9.1. Randomisation will occur within 2 weeks (+/- 1 week) after screening. All other visits will be scheduled from the date of randomisation or from the day of initiation of the study drug if the initiation of the study drug is delayed for more than 7 days for drug-specific logistical reasons (e.g. vaccination requirements before the initiation of a study drug).

If it is not possible to complete some of the study assessments at a visit, for example due to ill health, then results obtained as part of routine clinical care can be used, if collected during the appointment window as defined in Section 9.1. The values obtained from the medical records should be entered in the CRF with the date they were collected.

At 12 months, a review of survival status will be completed and participants are informed of this in the PIS. Ideally this will be confirmed without requiring further contact with the participant (refer to study-specific research manual for more details). Survival status may be confirmed by reviewing hospital records or by contacting the participant's GP to review their records.

## 9.3 Unscheduled visits

An unscheduled visit or video/telephone call may be arranged if an IMP is found to be futile and is dropped from the study in order to discuss the next steps with the participant. Refer to section 9.10 for details.

Other unscheduled visits or video/telephone calls may be arranged at the discretion of the local study team, for example if the participant contacts the team with a medical concern about the study.

## 9.4 Procedures for assessing efficacy

## NFL

As described in Section 8.1, the primary outcome is blood NFL levels as a surrogate outcome for biological efficacy. Blood samples will be collected, processed and stored at site before being shipped in batches to EXPERTS-ALS Oxford Laboratory, for analysis. The sample handling procedures will be fully described in a study-specific Sample Collection SOP.

## 9.5 Procedures for clinical assessments

## ENCALS Risk Score

The ENCALS risk score (13) must be calculated at screening and is used to determine eligibility. Details of how to access the online calculator and document the risk score are provided in the study-specific research manual. The following clinical variables are required for risk estimation: date of birth, date of ALS diagnosis, date of ALS symptom onset, date of screening, ALSFRS-R total score at screening, FVC % predicted at screening (according to GLI-2012), site of ALS symptom onset, El Escorial diagnostic criteria category and presence of ALS-FTD. If a patient is unable to generate a FVC measurement, Slow vital capacity (SVC) can be measured instead, and SVC % predicted at screening can be used to calculate the risk estimation instead of FVC % predicted. The risk profile is based on the ENCALS survival model and can be conceptualised as a relative summary of prognostic information. The risk profile indicates how participants compare to each other (i.e., who is faster or slower

progressing than average) without estimating the absolute survival time or probability.

#### ALS Functional Rating Scale Revised (ALSFRS-R)

The ALS functional rating scale revised (ALSFRS-R) (18) score is an investigator-administered function-based symptom questionnaire that can be used as an indicator of disease progression. It comprises 12 questions examining lower limb, upper limb, bulbar and respiratory function. Each question scores between 0 and 4 points with a maximum overall score of 48 (higher scores indicate better function). Staff training will be provided and the full procedure is detailed in the study-specific research manual.

#### Forced Vital Capacity (FVC)

Forced vital capacity (FVC) is the measurement of the total volume of air exhaled following full inspiration and is used to measure the strength of the respiratory muscles. Seated FVC will be assessed. Participants will be asked to inhale as far as possible then exhale quickly into a spirometer using a mask held firmly over the nose by the assessor (rather than a mouthpiece to overcome issues with lip seal due to bulbar dysfunction) until all air is exhaled. A minimum of three and a maximum of five trials will be completed and the best will be recorded. The measurement is adjusted for height and age. Staff training will be provided and the full procedure is detailed in the study-specific research manual.

#### Peak cough flow (PCF)

Peak cough flow (PCF) will be measured using the spirometer used to measure in-clinic FVC or a Wright's peak flow meter. A facemask will be held firmly over the participants nose and mouth by the assessor. Participants will be instructed to inhale to a maximum capacity and then forcibly cough through the oronasal facemask in a seated position. Three to five measurements will be taken. The maximum score will be recorded in litres per minute (L/min). A score of less than 60 is recorded as 0 L/min if using a Wright Peak FLow Meter and a score of greater than 880 L/min, recorded as 881L/min (19).

#### King's Stage

Disease staging will be completed using the King's staging system (20,21). It describes several key steps in the disease progression of MND including functional involvement of one, two or three CNS regions and need for gastrostomy or non-invasive ventilation. The stages are defined as follows:

- Stage 1: Symptom onset (involvement of first region)
- Stage 2: Involvement of a second region
- Stage 3: Involvement of a third region
- Stage 4A: Need for gastrostomy
- Stage 4B: Need for respiratory support (non-invasive ventilation)

Assigning participants to a stage can be done from assessment of the medical records or using standard questions and neurological examination. Staff training will be provided and the full procedure is detailed in the study-specific research manual.

#### Edinburgh Cognitive and Behavioural ALS Screen (ECAS)

The Edinburgh cognitive and behavioural ALS screen (ECAS) is a 130-point cognitive screening tool that is adapted for use in people with difficulty communicating or writing due to muscle weakness. It takes 15-20 minutes to complete. The ECAS will be administered face-to-face by a delegate trained in its use. Part of the ECAS is a behavioural screen which

involves a semi-structured interview with a relative/carer or friend of the participant completed independently of the participant. Ideally the behavioural screen will be completed face-to-face but it can be completed by telephone if necessary. The behavioural screen should be completed within 2 weeks of the participant ECAS. This part of the assessment will only be completed if consent has been provided by the participant and the relative/carer.

The ALS-specific score is out of 100 and the non-ALS-specific score is out of 36. An ECAS total score is produced by summing these scores together to give a maximum score of 136. The thresholds for 'normal' scores can be found in the guidelines (22). In the UK, the threshold for ECAS total is 105 and a score at, or below, 105 suggests potential cognitive impairment.

#### WHODAS 2.0

The WHODAS 2.0 is a generic self-assessment instrument for health and disability covering 6 domains of functioning (cognition, mobility, self-care, getting along, life activities and participation). Each item scores between 1 and 5 with higher scores indicating greater disability. The 36-item self-administered version of the questionnaire will be used (or 32-item if the participant is not working), as this is suggested to be the optimum amount of information (23).

#### 9.6 Procedures for assessing safety

Adverse events will be recorded in the medical notes and case report form. Refer to Section 10 for full details. If there are any clinical concerns about a participant, identified through any of the research procedures or assessments, these will be referred to the appropriate clinical team for further investigation. This includes abnormal blood results, responses to questionnaires that cause concern about the participant's wellbeing, and any other concerns aside from the expected course of ALS.

The safety assessments listed below will be completed as per the study assessments schedule in Section 9.1. The assessments may be completed at additional timepoints if clinically indicated. Where additional IMP-specific monitoring is required, this will be detailed in the IMP-specific appendices.

#### Safety bloods

Blood samples will be taken as per the timings in the Study Assessments Schedule in 9.1. The samples will be analysed locally and the following parameters measured:

- Full blood count (FBC) including Haemoglobin (Hb), white blood count (WBC), lymphocytes, neutrophils and platelets
- Liver function tests (LFTs) including ALT, AST, ALP, bilirubin and GGT
- Renal function including sodium, potassium, eGFR

Where additional IMP-specific monitoring is required, this will be detailed in the IMP-specific appendices.

#### Vital signs

Blood pressure, heart rate, weight, respiratory rate and height (screening only) will be measured. Where additional IMP-specific monitoring is required, this will be detailed in the IMP-specific appendices.

## Physical examination

A physical examination will be completed and non-ALS abnormalities will be recorded.

## 9.7 Procedures for assessing quality of life

Questionnaires will be provided in print to the participant for self-completion. Data from the paper questionnaires will be entered onto the study database by the local research team. At the time of completion, questions may be clarified for the participant if the question is not understood, but the researcher will not provide any bias towards any of the answer options.

## WHOQOL-bref

Quality of life (QoL) will be assessed via the WHOQOL-bref (24) which is a self-administered questionnaire comprising 26 questions on the individual's perceptions of their health and wellbeing over the previous two weeks. The responses to questions are on a 1-5 Likert scale and it produces four domain scores (physical, psychosocial, social relationships and environment. Higher domain scores indicate higher quality of life.

## 9.8 Procedures for sample and data collection for future research

Whole blood, plasma, serum, urine and stool samples will be collected from all participants as per the study assessments schedule. An overnight fasting period is required for the blood samples collected at baseline and week 12. Stool sample collection kits will be provided to participants at the screening, baseline and week 12 visits and participants will be asked to return a sample to the EXPERTS-ALS UCL Laboratory via a pre-paid envelope prior to baseline, week 12 and week 24 (or early discontinuation of treatment). The stool sample should be completed the day before the visit. Participants will complete a food diary over the three days leading up to each stool sample collection. At the screening, week 12 and week 24 (or early discontinuation of treatment) visits, participants will be asked to complete a lifestyle questionnaire. Samples will be processed and stored locally prior to shipping in accordance with the study-specific sample collection SOP. Samples will be shipped in batches to EXPERTS-ALS Oxford Laboratory and EXPERTS-ALS UCL Laboratory, and stored for future research. Access to samples for future research will be subject to a review by the EXPERTS-ALS WS3 committee in accordance with the relevant study specific SOP.

Future studies will include whole genome sequencing, completed at King's College London, on an anonymised basis, without individual feedback of genotype, for which there is a separate clinical pathway. Stool samples and the associated food diaries and lifestyle questionnaires will be used in future research to understand how the microbiome affects IMP response. Participants are informed of this in the PIS.

The maximum quantity of blood to be taken within a 24 hour period is 90 ml.

## 9.9 Procedures for remote respiratory function assessments

Currently the primary measures of respiratory function (FVC and PCF) require in-person measurements. This is burdensome on patients and clinical trials. These measures are volitional and rely on good technique which is often difficult for people with MND due to bulbar and limb dysfunction. They may be affected by the fatigue associated with travel to trial visits. Conversely, problems with technique may affect unsupervised assessments. Athome measures of FVC can be undertaken using handheld spirometers such as the Spirobank smart which can record FVC and provide qualitative data using a flow volume loop. These have been used in small case studies but are not currently validated for either

supervised or unsupervised use and therefore are not currently acceptable trial outcome measures. There are no at-home PCF devices but the Mini-Wright Standard Peak Flow Meter provides a basic measure of peak expiratory flow volume and may be an appropriate surrogate marker of PCF.

#### Remote Forced Vital Capacity (rFVC)

Those participants able to generate an FVC in clinic and who have a smartphone will be provided with a spirometer to allow FVC to be measured remotely (rFVC). They do not require access to the internet to complete the assessments. They will conduct a maximum of three measurements of unsupervised seated rFVC on each assessment.

The MIR Spirobank Oxi spirometer with a mask and filter will be used. The Spirobank Oxi connects using bluetooth to the participant's smartphone (no internet connection is required). Participants will be provided with diaries in which to log their results which will be collected at each visit. The results and flow volume loops are stored within the app on the phone and downloaded at each clinic visit.

Participants will be trained to use the Spirobank Oxi in person. Instructional videos and paper guides will show the participants the correct technique. During training sessions they will complete up to three supervised attempts. The instructor will then leave the room and the participant will complete a further three attempts. All scores will be recorded. Participants will be trained face to face at screening and again at baseline. At week 4 the study team will contact the patient by telephone or video and collect the remote scores. If the patient's week 4 scores are not within 150mls of their baseline FVC, further coaching and review of the flow-volume loops will be given by video or telephone.

In the event the participant is unable to generate any acceptable FVC, rFVC, PCF or rPCF (typically due to bulbar dysfunction) they will not be given a device. Site staff will record reason(s) why patients are not given a spirometer or PCF machine.

Participants will complete rFVC as per the schedule. Participants will be asked to conduct rFVC within a seven day window before or after their follow up visit (remote or in person).

#### Remote Peak cough flow (rPCF)

Participants able to provide at least three PCFs will be provided with a Wright Peak Flow Meter and mask. The same training and testing schedule as rFVC will be used. The participants will record the results in a diary as the devices do not use a smartphone.

#### Data collection

Patients will record the results for rFVC and rPCF in a diary. The rFVC data is collected by the Spirobank app and stored on the phone using the participant's study ID and date of birth only. Each recording result will be saved as a PDF by the participant during a study visit with assistance from the local study team as needed. The PDFs will be transferred to the study site via email (or via bluetooth transfer, if required) and the local study team will assist the participant to do this during a study visit. PDFs will be stored locally at site before being securely transferred to The University of Sheffield for analysis.

### 9.10 Participant withdrawals

#### Early discontinuation of treatment

Participants may wish to discontinue study treatment, the treatment arm may be dropped from the study for futility, or there may be a clinical need to discontinue it. If this occurs, it will be documented on an intervention withdrawal form and in the patient notes. If applicable, a pregnancy test will be completed at treatment discontinuation or at the next study visit as per Section 9.1. The study assessments schedule in Section 9.1 provides details of other assessments to be completed at treatment discontinuation (or at the next study visit). Early discontinuation of treatment does not constitute withdrawal. Participants discontinuing treatment early should continue in the study as normal for follow up if they are willing, apart from intervention administration. Follow up would include scheduled study visits up to week 24 (as per the study assessment schedule) and allowing the study team to access their medical records and any relevant hospital data that is recorded as part of routine care.

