### 8. Outcomes

#### 8.1 Primary outcome/endpoint

Change in blood NFL levels from baseline to weeks 18 and 24.

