- b. Week 4 and week 8 visits may be completed remotely unless there are IMP specific monitoring requirements as detailed in the IMP specific appendices. Study drug dispensing and accountability are not required for remote visits.
- c. An early discontinuation of treatment (EDoT) visit should be completed for participants stopping study treatment early. This may be completed at the same time as another scheduled visit or as a separate visit at the discretion of the local investigator. If a participant stops study treatment early but remains in the study for follow-up, the following assessments do not need to be repeated at week 24 if they are completed at EDoT: pregnancy test, WHODAS 2.0 and WHOQOL-BREF.
- d. Refer to section 5.5 for details.

- e. Persons of childbearing potential must have a negative pregnancy test prior to randomisation (at the baseline visit or within 7 days prior to baseline) and at treatment discontinuation or at the next study visit (see Section 5.8 for definitions). Additional testing may be required for individual IMPs, refer to the IMP specific appendices for details.
- f. As per section 9.6 the following parameters will be measured: Full blood count including haemoglobin, white blood count, lymphocytes, neutrophils and platelets; liver function tests including ALT, AST, ALP, bilirubin and GGT; renal function tests including sodium, potassium and eGFR.
- g. Determined by IMP under investigation refer to the IMP-specific appendix for details.
- h. Test can be completed +/- 7 days around appointment date.
- i. Face-to-face training provided for participants at screening and baseline visits.
- j. Conducted at same time as standard FVC/peak cough flow.
- k. Remote training provided for participants at week 4.
- I. An overnight fasting period is required for the blood samples collected at the baseline and week 12 visits.
- m. A food diary will be completed by the participant over the three days leading up to the stool sample collection. The local study team will record in the database whether the diary has been completed or not but the data will not be entered into the trial database. Paper copies of the diary will be stored securely by the participating site.

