#### Dealing with missing outcome data

The Bayesian linear model will implicitly account for missing outcome data if a patient has at least one of the two NFL levels at 18 or 24 weeks ascertained. If more than 10% of patients in an arm have both NFL levels at 18 and 24 weeks missing, we will use a multivariable Bayesian prediction model that incorporates baseline characteristics, NFL levels pre-randomisation, intermediate NFL levels ascertained at 12 weeks, available NFL levels observed at 18 and 24 weeks and clinical outcomes to derive posterior predictive distributions that allow estimation of pairwise between-group mean differences in NFL levels at 18 to 24 weeks with 95% credible intervals and Bayesian posterior probabilities of non-inferiority or superiority and arm-specific mean changes from baseline with 95% credible intervals and posterior probabilities to reach a reduction from baseline.

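### The early-discontinuation visit draws research blood but no NFL sample, so a participant who stops the drug and declines later visits may have no NFL value after baseline, or none after week 12

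*Protocol*

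**What the plan says.** Section 9.10 names a pregnancy test at treatment discontinuation and leaves the rest to the schedule: "The study assessments schedule in Section 9.1 provides details of other assessments to be completed at treatment discontinuation (or at the next study visit". Footnote c to Table 2 (Section 9.1) requires the visit: "An early discontinuation of treatment (EDoT) visit should be completed for participants stopping study treatment early". On timing it adds: "This may be completed at the same time as another scheduled visit or as a separate visit at the discretion of the local investigator".

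The EDoT column of Table 2 is marked for the pregnancy test, IMP-specific monitoring, WHODAS 2.0, WHOQOL-BREF, drug accountability, research blood and stool, the lifestyle questionnaire, the food diary and the spirometer reports. It is empty for NFL sampling and for ALSFRS-R.

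The primary endpoint in Section 8.1 is "Change in blood NFL levels from baseline to weeks 18 and 24", analysed by intention to treat (Section 11.1). Stopping treatment is not withdrawal: "Participants discontinuing treatment early should continue in the study as normal for follow up if they are willing, apart from intervention administration". Section 2.4 says that participants in an arm dropped for futility come off treatment and may remain for follow-up.

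On the research samples, Section 9.8 says: "Whole blood, plasma, serum, urine and stool samples will be collected from all participants as per the study assessments schedule". They are stored for later studies, and no NFL assay for the trial is attached to them.

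Section 11.1 uses week 12 NFL as the intermediate value in the futility prediction model. It uses it again in the missing-outcome model, which applies under this condition: "If more than 10% of patients in an arm have both NFL levels at 18 and 24 weeks missing".

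**The concern.** The EDoT visit already includes a blood draw, but the tube needed for the primary outcome is not among those collected. For a participant who will not come back, it is the last chance to obtain an NFL value at or near the end of exposure. Without that value, the two prediction models in Section 11.1 must represent the participant from baseline NFL, baseline characteristics and whatever clinical data exist, and from week 12 NFL if the stop came later. Stopping is plausibly related to tolerability and progression, so these participants need not resemble those who stay.

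The same visit applies when an arm is dropped for futility. Section 11.1 still requires that arm's mean change from baseline to be estimated, and the drug to be ranked, whatever conclusion was reached. A statistical analysis plan cannot repair this, because a sample that was not drawn cannot be analysed.

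**Working it through.** **1. Reading of Table 2.** Each row has nine visit columns.

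| Row | Visits marked |
|---|---|
| NFL sampling | -2, 0, 12, 18, 24 |
| ALSFRS-R | -2, 0, 8, 12, 18, 24 |
| Research blood | 0, 12, 24, EDoT |
| Pregnancy test, WHODAS 2.0, WHOQOL-BREF | 0, 24, EDoT |

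As a check on column alignment, footnote c says "the following assessments do not need to be repeated at week 24 if they are completed at EDoT: pregnancy test, WHODAS 2.0 and WHOQOL-BREF". The three assessments it names are marked at EDoT in the table, so the empty NFL cell is not an artefact of reading the columns.

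**2. NFL values available, by time of stopping.** This assumes a separate EDoT visit and refusal of all later visits.

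- Stop before week 12: 2 baseline values, 0 afterwards.
- Stop between weeks 12 and 18: 2 baseline values plus week 12.
- Stop after week 18: 2 baseline values plus weeks 12 and 18, so the endpoint is partly observed.

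If the participant stays in follow-up, or EDoT is combined with week 12, 18 or 24, NFL is drawn at the scheduled visit.

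**3. Arms dropped for futility (counts from Section 11.2).**

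- Futility analysis 1: about 28 randomised, at least 23 at week 12, at least 16 at week 18. Not yet at week 12: up to 28 - 23 = 5. Not yet at week 18: up to 28 - 16 = 12, and 12/28 = 43%.
- Futility analysis 2: about 35 randomised, at least 29 at week 12, at least 20 at week 18. Not yet at week 12: up to 35 - 29 = 6. Not yet at week 18: up to 35 - 20 = 15, and 15/35 = 43%.

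Some will pass these weeks before the decision takes effect. On the other side, Section 11.2 says that the number randomised will be somewhat higher in the first phase of the platform.

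**4. The plan's power statement.** Section 11.2 claims more than 80% power with 80 per arm for a margin or true difference of 0.10 log10 units. Inputs are SD 0.35, correlation 0.80 (stated for the futility analyses and assumed here) and one-sided 0.025, as a frequentist approximation to the Bayesian rule: power = Φ(0.10 / (SD × √(2/80)) - 1.96).

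- Change score: SD = 0.35 × √(2 × (1 - 0.80)) = 0.2214, power 81.5%.
- Baseline-adjusted: SD = 0.35 × √(1 - 0.64) = 0.210, power 85.4%.
- Means of two baseline and two follow-up values, compound symmetry: SD = 0.152, power 98.6%.

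The claim is reproduced. If 10% of each arm contributed nothing (72 per arm), the three figures would be 77.4%, 81.5% and 97.6%. At 20% (64 per arm) they would be 72.4%, 76.8% and 96.1%. Those losses come from missing endpoint values, which an EDoT sample would not restore.

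**5. The 10% trigger.** Section 12.1 cites past attrition of over 20% in MND trials. As an assumption, let 20% of an 80-patient arm stop early: 80 × 0.20 = 16. If none to all of them decline later visits, between 0 and 16 lack both values (0% to 20%). Half gives 8/80 = 10%, which does not exceed the trigger. Nine would: 9/80 = 11.25%.

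**The case against.** The strongest reply is that the schedule contains no error. The endpoint is intention to treat at weeks 18 and 24, and the protocol's policy for early stoppers is the matching one: keep them in follow-up. Section 9.10 also asks centres to explain why staying matters. An EDoT value is not an endpoint value. It also helps least where the gap is widest. Section 4 says that up to 6 months may be needed before an NFL endpoint can be detected, so a sample after a few weeks of titration adds little to two baseline values whose correlation with later values is high (0.85 or more in the dataset cited in Section 11.2). Someone who stops at week 15 already has the week 12 value that the models name. EDoT assessments may also wait until the next visit, when the sample could be well off drug.

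All of this stands, and it limits the point to participants who attend a separate EDoT visit and then decline later NFL visits. It does not remove the point. For those participants the tube is the only further NFL information obtainable, and Section 11.1 needs estimates for dropped arms as well as retained ones.

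A reader might go further and infer any of the following, none of which the documents support:

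- That the trial is underpowered. Step 4 reproduces the stated power.
- That the models must use baseline NFL alone. Section 11.1 also gives them baseline characteristics, and the missing-outcome model uses clinical outcomes.
- That attrition at the cited level would invoke the missing-outcome model. That depends on an unknown share declining visits. The cited figure is also historical attrition, not treatment stopping, and Section 12.1 says that this design's effect on attrition is unknown.
- That the missing ALSFRS-R is an equal gap. ALSFRS-R is also scheduled at week 8, and the secondary outcome is change to weeks 12 and 24, which an EDoT score would not supply.

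**Conclusion.** The point holds as a gap in data collection that is inexpensive to close. Participants who stop drug, attend a separate EDoT visit and decline later visits leave no NFL value after baseline if they stop before week 12, and only week 12 if they stop between weeks 12 and 18. The group that could be affected when an arm is dropped is up to about 12 of 28 or 15 of 35 at the analysis cut. How many of them would decline follow-up is not known, so the effect on bias or precision cannot be stated.

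The benefit is bounded. An EDoT value would inform the interim prediction model, and the final missing-outcome model when more than 10% of an arm lacks both endpoint values. At or below 10%, Section 11.1 gives such a value no role. No stated power or sample size needs correcting.

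**What to change.** In Table 2, mark NFL sampling in the EDoT column, with a footnote that it applies when EDoT does not coincide with a scheduled NFL visit. Draw the tube with the EDoT research blood and record the date of last dose. In Section 11.1, let the prediction and missing-data models take the value at its actual week as an auxiliary intermediate NFL measurement. State that it does not replace the week 18 or 24 samples in anyone who continues. ALSFRS-R at EDoT is optional.

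The cost is one tube at a venepuncture already scheduled, one assay per eligible visit, and a protocol amendment. The assays are not confined to tolerability stoppers, because everyone still on treatment when an arm is dropped would qualify. As a high-end illustration, if all 20 drugs that Section 11.2 allows for were dropped at the first futility analysis, 20 × 12 = 240 participants short of week 18 could need one, plus those between weeks 18 and 24. The routine load is at most 700 × 5 = 3,500 samples, so the 240 would add about 7%. The analysis also gains an irregularly timed covariate, which carries little information for very early stops.
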